As abnormal concentrations of blood lipids can result from changes in the production, conversion or clearance of lipoprotein particle, static measurements of lipid levels do not reveal the underlying mechanism of these lipid disorders. Therefore it is necessary to confirm the effects of GLP-1 agonists on the kinetics of TG, apo-B48 and apo-B100 in the postprandial state using stable isotopes concomitantly with quantification of liver fat to demonstrate how GLP-1 system modulates lipoprotein metabolism in T2DM. Kinetic studies in humans provide an important and unique tool to quantitatively elucidate the dynamics of lipid metabolism providing estimates of lipoprotein secretion and clearance underlining the pathophysiology of lipid disorders.

We have established and validated novel gas chromatography/mass spectrometry (GC/MS) methods to analyze the enrichment of combined load of stable isotopes; ²H₅ glycerol, to track enrichments into VLDL-TG, ²H₃leucine incorporated to apo-B48 and apo-B100, ¹³C₄palmitate a to track the contribution of dietary lipids to VLDL triglyceride secretion and ²H₂O heavy water to quantitate DNL in the VLDL particles released by liver (Table 1, Figure 2).

Stable isotopes
²H₅-Glycerol Injected tracer that is esterified to triglycerides in the liver but not the intestine as it lacks glycerol kinase activity. It is thus only incorporated into VLDL–triglycerides.
²H₃-Leucine Injected tracer that is incorporated into apoB100 and apoB48. Chylomicrons secreted from the enterocytes contain apoB48, while VLDL secreted from the liver contain apoB100.
¹³C₄-Palmitate The dietary tracer [1,2,3,4- ¹³ C]-palmitate will be served in the meal to track the contribution of dietary lipids to VLDL–triglyceride secretion.
²H₂O (heavy water) Given orally. Incorporated into all fatty acids. Used to quantify the amount of fatty acids derived from liver de novo lipogenesis into VLDL ₁ and VLDL ₂ .

[figure not shown]

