Figure 2. Outline of a kinetic study that includes three major steps: (i) clinical visit protocol, (ii) sample preparation/processing and enrichment analysis by GC/MS, and (iii) mathematical modeling. Subjects ingest heavy water and ¹³C₄-Palmitate and receive infusions of ²H₅-Glycerol and ²H₃-Leucine (Table 1). After GC/MS-detection of stable isotope enrichments in isolated lipoprotein fractions it is possible to mathematically follow the metabolism of both dietary and endogenous derived triglycerides, apoB-100 and apoB-48 and calculate the amount of de novo –lipogenesis in TRL fractions.

In the development of the model we have utilized the data from 5 subjects who have had a kinetic study (1) in the fasting state and (2) repeated together with an oral fat load test. We have established for the first time that our protocol allows us to follow the production, transfer and direct catabolism of hepatic (VLDL₁ and VLDL₂) and intestinal (chylomicrons) lipoprotein particles and triglycerides in vivo, and to elucidate how DNL and dietary lipids contribute to postprandial TRLs. We also have demonstrated that our new non-steady state model allows the mathematical modeling of the data.

RESEARCH HYPOTHESIS

[figure not shown]
The aim of this study is to elucidate the mechanisms underlying the positive effect of incretin therapy on lipoprotein metabolism in type 2 diabetic subjects and for the first time establish the potential effect on liver DNL. Our study design allows differentiating the impact of weight loss dependent and independent effects of liraglutide on lipoprotein and carbohydrate metabolism.

We hypothesize that:

1. Reversal of the incretin defect by liraglutide will result in reduced production and/or improved clearance rate of chylomicrons and remnants
2. GLP-1 receptor activation in the liver will be associated with decreased hepatic DNL, consequently, reduced production of large VLDL₁ particles and decrease in liver fat content.
3. Positive effects of liraglutide on TRL kinetics and liver fat are further potentiated with weight loss.

TREATMENT

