Tracer labelling. On the evening of the first visit, $^2\text{H}_2\text{O}$ (2 g/kg) will be given between 18:00 and 22:00 to assess the contribution of de novo lipogenesis to fatty acids in VLDL (Figure 3). At 8:00 the following morning, the subjects will receive a bolus injection of $^2\text{H}_5$ -glycerol (500 mg) to assess the VLDL-triglyceride kinetics, and a bolus injection of $^2\text{H}_3$ -leucine (7 mg/kg) to assess VLDL-apoB100 and chylomicron-apoB48 kinetics. The fat rich mixed meal (57 g fat, 63 g carbohydrates and 40 g protein, total 934 kcal) with $^{13}\text{C}_4$ -palmitate tracers (1-2 g) is served 2 h after the infusions begins.

Sampling and sample preparation. Blood samples will be taken at frequent time points as indicated by the red dots (Figure 4) and lipoprotein fractions (chylomicrons, VLDL₁ and VLDL₂) will be separated by density gradient ultracentrifugation (DGU). Concentrations of lipids and apolipoproteins (apo-B100, apo-B48) will be measured in whole plasma and in all fractions at each time point.

Quantification of lipoprotein fluxes. Enrichments of isotopes in lipids (TG, FAs) and in apo-B100 and apo-B48 are determined by GC/MS [28] and/or by proteomics [29] at each time point (red dots). Hepatic DNL is calculated from enrichment of deuterated water ingested during the kinetic study at specified time points (0, 4 and 8 hrs.) [30]. We will use a novel multicompartmental model to describe the fluxes of materials combining apoB100 and apoB48 kinetics [7, 28, 29].

2. Determination of liver, subcutaneous and intra-abdominal fat. Using standardized protocols, we will perform a proton magnetic resonance spectroscopy (MRS) to determine liver fat content and magnetic resonance imaging to determine subcutaneous abdominal and intra-abdominal fat. [31]

3. Lipolytic enzymes, advanced lipid analysis, fat biopsies and genetic studies. We will analyze mass and enzyme activity of LPL and hepatic lipase after an injection of 75 IU/kg heparin. RLP-TG and RLP-cholesterol will be measured at 0, 4, and 8 hrs. A fasting sample is obtained for LDL and HDL size determination.

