The study continues until 13 subjects have completed in both arms. Subjects completing the protocol are included to the statistical analyses. Paired t-test (within group) and ancova (treatment effect) will be used. The number of subjects needed is based on previous studies and are in accordance with a recently published article showing that a 25% difference in VLDL kinetics can be detected with 9 subjects per each group [33].

PRIMARY OBJECTIVE

1) To examine the effect of 16 weeks of treatment with liraglutide on triglycerides (TG) and apoB48 production rates (PR) and/or fractional catabolic rates (FRC) in the lipoprotein fraction chylomicrons ($S_f > 400$) in patients with T2DM treated with metformin. This will be fulfilled by kinetic modeling during a standardized fat-rich mixed-meal test combined with stable isotope administration.

2) To evaluate the for the first time in humans the effect of 16 weeks of treatment with liraglutide compared to baseline on hepatic DNL and liver fat content in patients with T2DM treated with metformin, assessed during a standardized fat-rich mixed meal test.

SECONDARY OBJECTIVES

To evaluate the effect of 16 weeks of treatment with liraglutide compared to baseline in patients with T2DM treated with metformin, assessed during a standardized fat-rich mixed-meal test combined with stable isotope administration on:

- production rates (PR) of TG, apo-B48 and apo-B100 in the lipoprotein fractions VLDL₁ (Sf 60–400) and VLDL₂ (Sf 20–60)
- fractional catabolic rates (FCRs) of TG, ap-B48 and apo-B100 in the lipoprotein fraction VLDL₁ (Sf 60–400) and VLDL₂ (sf 20–60)
- fasting and postprandial serum total TG, total cholesterol, and total apo-B, apo-B48, RLP-chol and RLP-TG, apo-CIII and apo-A5 as well as fasting LDL and HDL size. RLP-chol and RLP-TG are surrogate markers of remnants. Apo-CIII and apo-A5 are key regulators of the lipolytic cascade.
- TRL clearance assessed as effect on post-heparin lipoprotein lipase (LPL) and hepatic lipase (HL) activities. LPL and HL are the key enzymes regulating lipolysis of TRLs and remnant removal by the liver.
- fasting and postprandial glucose, insulin and C-peptide, assessed also during an OGTT.
- fasting visceral and subcutaneous fat depots assessed by MRS in both fasting and in postprandial period.

SAFETY REPORTING

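### Primary objective 2 and the secondary objectives are worded against baseline, no test is named as deciding any objective, and the six named primary quantities have no error control

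*Combined protocol and SAP*

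**What the plan says.** **Design.** Under TREATMENT, patients are randomized to liraglutide with free diet or to placebo with a dietician-supervised loss of 3.0 kg. The stated purpose is similar weight loss in both arms; earlier liraglutide studies are said to show 3 to 3.5 kg. RESEARCH HYPOTHESIS says the design separates weight-dependent from weight-independent effects of the drug. Hypothesis 3 reads "Positive effects of liraglutide on TRL kinetics and liver fat are further potentiated with weight loss".

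**Objectives.** Primary objective 1 concerns "triglycerides (TG) and apoB48 production rates (PR) and/or fractional catabolic rates (FRC) in the lipoprotein fraction chylomicrons" and names no comparator. Primary objective 2 concerns "the effect of 16 weeks of treatment with liraglutide compared to baseline on hepatic DNL and liver fat content". The SECONDARY OBJECTIVES also take baseline as the comparator. They include "production rates (PR) of TG, apo-B48 and apo-B100 in the lipoprotein fractions" VLDL1 and VLDL2, and VLDL1 production is part of hypothesis 2.

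**Analysis.** STATISTICAL METHODS AND POWER gives the tests in one sentence: "Paired t-test (within group) and ancova (treatment effect) will be used". It states no alpha, order, co-primary rule or multiplicity adjustment. The study runs until 13 subjects per arm have completed. That number is said to rest on previous studies and to agree with a published article "showing that a 25% difference in VLDL kinetics can be detected with 9 subjects per each group".

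**DNL.** STUDY PROTOCOL, item 1, calculates hepatic DNL at 0, 4 and 8 hours, and the stable-isotope table refers to both VLDL1 and VLDL2. The supplied text does not say which value is primary. Appendix A, cited for analysis detail, is not in the supplied text.

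**The concern.** Both arms are meant to lose about 3 kg, and the protocol itself expects weight loss to act on liver fat. A change from baseline in the liraglutide arm is therefore drug effect plus weight loss. Only the contrast with the placebo weight-loss arm can separate the two, and only so far as weight loss really is similar. Followed literally, objective 2 could be declared met on a change that placebo patients share. That would contradict the stated aim of the design.

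The second problem is what counts as success. Six quantities carry the label primary: TG production rate (PR), TG fractional catabolic rate (FCR), apoB48 PR and apoB48 FCR in chylomicrons, hepatic DNL, and liver fat. With no rule for combining them, any one nominally significant result could be presented as a positive primary finding.

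**Working it through.** **Inputs from the protocol:** 13 completers per arm; paired t-test and ANCOVA; six named primary quantities; 25% with 9 per group for VLDL kinetics. **Assumptions, because the protocol gives no figure:** two-sided 0.05 per test, 80% power, the size of the weight-loss shift, the correlation between outcomes, and residual SDs.

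**1. The plan's own figure.** The 25% with 9 per group cannot be reproduced, since SD, alpha, power and paired or parallel design are not given. If it is a two-group comparison at 0.05 with 80% power (t distribution), the detectable standardized difference is 1.407, so the implied SD is 25 / 1.407 = 17.8% of the mean. With that SD, 13 per arm would give 93% power for 25% at 0.05 and 75% at 0.05/6. If the 9 are pairs, the implied SD of change is 23.4%. Either way the figure describes VLDL kinetics, which are secondary.

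**2. Within-arm test when the drug does nothing.** Let weight loss shift the outcome by s SDs of change in both arms. The paired t-test has 12 df, critical value 2.179 and noncentrality s × √13.

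| s (assumed) | noncentrality | P(paired test significant) | P(between-arm test significant) |
|---|---|---|---|
| 0.3 | 1.08 | 17% | 5% |
| 0.5 | 1.80 | 38% | 5% |
| 0.8 | 2.88 | 75% | 5% |
| 1.0 | 3.61 | 91% | 5% |

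The shared shift cancels in the between-arm comparison. A simulated ANCOVA with baseline correlation 0.5 gave 5.0 to 5.1% at the three larger shifts.

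**3. Six tests without adjustment, no between-arm effect.** If independent, 1 − 0.95^6 = 0.265. Simulated ANCOVAs with equal correlation gave 0.214 at 0.5 and 0.113 at 0.9. Holm across the six gave 0.049, 0.042 and 0.023 at correlations 0, 0.5 and 0.9.

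**4. Holm or a fixed order.** Hypothesis 1 allows an effect on production, on clearance, or on both. Suppose only the two chylomicron FCRs differ, each by 1.15 SD. A fixed order of TG PR, TG FCR, apoB48 PR, apoB48 FCR, DNL, liver fat must first pass a null TG PR, so it confirms TG FCR in only about 3 to 4% of trials. Bonferroni over six, a lower bound for Holm, finds at least one FCR in 61 to 78% (correlation 0.9 to 0).

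**5. What 13 per arm can detect.** With noncentrality d × √(13/2), 23 df and 80% power, d = 1.148 at 0.05 and 1.478 at 0.05/6. As a percentage of the mean:

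| residual SD (assumed) | at 0.05 | at 0.05/6 |
|---|---|---|
| 17.8% (step 1, VLDL only) | 1.148 × 17.8 = 20% | 1.478 × 17.8 = 26% |
| 20% | 23% | 30% |
| 30% | 34% | 44% |
| 40% | 46% | 59% |

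**The case against.** The strongest reply is that the ANCOVA is already planned and is the test labelled for the treatment effect. All subjects are measured before and after, so the reference to baseline may only mean that outcomes are changes from baseline, with the ANCOVA then comparing arms. This stands in part. A reader might infer that objective 2 is definitely to be judged by the paired t-test, or that no between-arm analysis is planned. The text supports neither. It does leave the choice open, and the wording of objective 2 leans towards the within-arm reading. Objective 1 has the same gap in milder form.

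A reader might also count more than six primary tests, by taking DNL separately at each time point and in each VLDL fraction, and quote a much higher error rate. The documents do not support that. DNL may be reduced to one estimate from the several samples, and Appendix A may say how. Independence is also unlikely: TG and apoB48 travel in the same particle, so the lower error rates are relevant too.

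Finally, this is a small mechanistic study, and the joining of production and clearance in objective 1 mirrors hypothesis 1. That argues against imposing a rigid order. It does not argue against an error rule for outcomes that the protocol itself calls primary.

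**Conclusion.** The concern holds in this form: the comparator wording does not match the design, no test is named as deciding, and six primary quantities have no error control. It should be corrected, although the needed analysis is already in the plan.

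The 38%, 75% and 91% apply only if the paired test decides, and they depend on the assumed shift. The 11 to 26% assumes 0.05 per test and equal correlation of 0.9 down to 0. The missing deciding test and error rule can be read directly from the text. The unfixed DNL summary is less certain while Appendix A is unseen.

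A reader might go on to infer that 13 per arm is too few, or that the cited 25% figure is wrong. Neither follows. The protocol gives no SD for any primary outcome, the basis of the cited figure cannot be checked, and the number is also said to rest on previous studies. One can say only that the stated figure is not about the primary outcomes.

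**What to change.** 1. In primary objectives 1 and 2 and in the secondary objectives, name the placebo weight-loss arm as the comparator. Add to STATISTICAL METHODS AND POWER: *For every objective the deciding test is the between-arm ANCOVA of the 16-week value adjusted for baseline. Within-arm paired t-tests are reported with 95% confidence intervals as descriptive estimates of total change.*

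2. List the six primary outcomes by name, with one DNL summary (time point or combination, and VLDL fraction). Apply Holm across the six at two-sided 0.05, which lets either production or clearance succeed. Use a fixed order only if the sponsor can justify one before any outcome data are analysed.

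3. Optional: state that the cited 25% concerns VLDL kinetics and not the primary outcomes, and that 13 completers per arm give 80% power for about 1.15 residual SD at two-sided 0.05 (about 1.48 SD at 0.05/6). Do not state what the cited article supports, and leave the sample size as it is.

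**Cost.** No new patients, visits or samples. The total change under liraglutide becomes descriptive, which changes what objective 2 estimates if it was meant within arm. The between-arm test is less sensitive than the paired one, and Holm lowers power for each outcome. The sponsor must also commit to one DNL variable in advance.

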The study will be single blinded into two groups matched for age, sex and BMI in order to achieve similar weight loss in liraglutide and placebo arms. In addition to a fixed dose of metformin (2 g/day) and simvastatin (20 mg/day) treatments, patients will be assigned to liraglutide therapy once daily and randomized to liraglutide group with uncontrolled diet or to placebo group with weight loss of 3.0 kg supervised by the study dietician for 4 months (Figure 3). Previous studies in type 2 diabetes show that the average weight loss with liraglutide is 3-3.5 kg and stable weight is achieved within 3-3.5 months (LEAD1-6). The study cohort will comprise male and female (non-fertile or of child-bearing potential using a medically approved birth control method) with T2DM eligible for treatment with metformin or on stable dose of metformin.

INCLUSION CRITERIA

Obese subjects with T2D and a large waist (waist > 88 cm in women and > 92 cm in men, BMI 27–40 kg/m², triglycerides between 1.0 – 4.0 mmol/L and LDL < 4.5 mmol/l) treated with a lifestyle or metformin (any dose) (HbA1c 6.5-9%) and aged 30 – 75 years will be included. Subjects may or may not use statins. **Only subjects who sign an informed consent are included to the study.**

EXCLUSION CRITERIA

- Type 1 diabetes
- Apo E2/2 phenotype
- ALT/AST > 3x ULN
- GFR < 60 ml/min, clinically significant TSH outside normal range
- Lipid-lowering drugs other than statins within 6 months
- Treatment with pioglitazone, insulin, sulphonylureas, gliptines, glinides, SGLT-2 inhibitors or thiazide diuretics (at a dose of > 25 mg / day) within 6 months
- Blood pressure > 160 mmHg systolic and/or > 105 diastolic
- History of pancreatitis or stomach / other major bleeding, thyroid neoplasia, persistent hypothyroidism or persistent hyperthyroidism
- Any medical condition that puts the patient in the risk of dehydration
- Concurrent medical condition that may interfere with the interpretation of efficacy and safety data during the study.
- Females of childbearing potential who are not using adequate contraceptive methods
- Subjects who have experienced side-effects previously from GLP-1 agonists
- Non-compliance or withdrawal of consent
- **Any information or clinical event described in liraglutide SPC that is a contraindication for the use of liraglutide (http://www.ema.europa.eu/docs/en_GB/document_library/EPAR_-_Product_Information/human/001026/WC500050017.pdf)**

WHITHDRAWAL FROM THE STUDY

- Withdrawal of consent

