Thereafter the baseline visits will include an OGTT, heparin test, non-fasting kinetics and abdominal MRI investigation days. The investigational product (Liraglutide or placebo) will be given to the subjects together with detailed instructions about the usage and storage (**Shelf life 30 months. After first use: 1 month. Storage in a refrigerator (2°C - 8°C). Do not freeze. Store away from the freezer compartment.**) (in +2 - +8 degrees, opened product in +2 - +29 degrees) of the product during these visits. After the study period of total 4 months these investigations are repeated. In addition to the screening visit(s), the subjects will undergo 8 investigational visits. The subjects meet dietician after randomization. The follow-up about weight, diet and possible adverse events takes place with weekly phone calls/e-mail contacts by the study nurse/dietician/doctor. Subjects fill in dietary records for 3 days before and during the investigational drug. At week 8 after initiation of the treatment period a blood sample for safety is drawn, weight is recorded and the patient meets dietician/study nurse if necessary. In case of unsuccessful weight loss, weight loss > 1.5 kg/month or adverse events, an additional visit is arranged. The duration of the study is 1-1.5 month run in and 4 to 4.5 month investigational phase i.e. 5 to 6 months. The subjects will be followed by a phone call/e-mail/visit 2 weeks after the end of the treatment period.

STUDY PROTOCOL: We will combine the novel kinetic protocol developed by us with several advanced analyses to elucidate how incretins modulate postprandial lipidemia and hepatic DNL in T2D subjects. To specifically elucidate the impact of a GLP-1 agonist on postprandial lipid metabolism, we will perform kinetic studies on all study subjects before and after the 4-months intervention with the GLP-1 agonist.

[figure not shown]

Figure 4. Detailed schedule for lipoprotein kinetic assessment. Red dots represent plasma samples for kinetic data (glycerol, leucine and palmitate enrichment in TRL fractions) and green arrows illustrate time-points for plasma incretin (GLP-1, GIP), glucose and insulin sampling.

1. Kinetic study with stable isotopes combined with an oral fat load. This study is based on the novel protocol developed by us (Figure 4). A detailed description of analysis is given in **Appendix A**.

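### The objectives measure liraglutide against baseline or against no stated comparator, and the planned between-arm ANCOVA is not named as the test that decides them

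*Combined protocol and SAP*

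**What the plan says.** All references are to the combined protocol and SAP.

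- **Research Hypothesis.** The stated aim includes telling weight-dependent from weight-independent effects of liraglutide. Hypothesis 2 attributes lower hepatic DNL, lower VLDL₁ production and lower liver fat to GLP-1 receptor activation in the liver. Hypothesis 3 says that weight loss adds to the effects on lipoprotein kinetics and liver fat.
- **Treatment.** The groups are "matched for age, sex and BMI in order to achieve similar weight loss in liraglutide and placebo arms". Patients are "randomized to liraglutide group with uncontrolled diet or to placebo group with weight loss of 3.0 kg supervised by the study dietician". The same section expects that "the average weight loss with liraglutide is 3-3.5 kg".
- **Primary Objective, item 1.** It begins "To examine the effect of 16 weeks of treatment with liraglutide on triglycerides (TG) and apoB48 production rates (PR" and goes on to catabolic rates in chylomicrons. No comparator is given.
- **Primary Objective, item 2.** It concerns the "effect of 16 weeks of treatment with liraglutide compared to baseline on hepatic DNL and liver fat content".
- **Secondary Objectives, lead-in.** "To evaluate the effect of 16 weeks of treatment with liraglutide compared to baseline in patients with T2DM treated with metformin".
- **Statistical Methods and Power.** The only sentence on tests is "Paired t-test (within group) and ancova (treatment effect) will be used". Thirteen completers per arm are planned.

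No objective mentions placebo or a difference between arms.

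**The concern.** The control arm is built to change from baseline too, because its participants are supervised to lose 3.0 kg. The liraglutide arm is expected to lose 3 to 3.5 kg. A change from baseline within the liraglutide arm therefore combines any drug-specific effect with the effect of weight loss and of anything else common to both arms. Only the contrast with the placebo arm can separate them, and that separation is the reason the arm exists.

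As worded, objective 2 is answered by the within-arm change. The statistics sentence supplies a test for that change and a test for the between-arm contrast, but no rule on which one answers which objective. The risk is one of interpretation: a significant fall in DNL or liver fat on liraglutide could be reported as support for hypothesis 2 even if the placebo arm fell equally. Which result to emphasise could also be settled after the data are seen.

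**Working it through.** **1. The text.** The point rests on the wording, set side by side:

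| Element | Comparison it implies |
|---|---|
| Aim and hypothesis 2 | Between arms, weight loss held similar |
| Treatment section | Between arms, weight loss held similar |
| Primary objective 1 | Not stated |
| Primary objective 2 | Own baseline |
| Secondary lead-in | Own baseline |
| Paired t-test | Within group |
| ANCOVA | Treatment effect; outcome, covariates and objective not stated |

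The first two rows and the objectives do not match, and the last two rows do not settle which governs.

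**2. The plan's own size figure.** The plan cites a 25% difference in VLDL kinetics as detectable with 9 per group. This cannot be reproduced, because no SD, significance level or power is given and the text does not say whether the figure is within-subject or between-group. Assuming two-sided 0.05 and 80% power, solving for the SD gives:

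- read as two-sample: SD 17.8%, and 13 per arm then gives 93% between-arm power for 25%;
- read as paired: SD of change 23.4%, and 13 then gives 94% for the paired test but 74% between arms.

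The choice of contrast therefore also affects what the sample size supports.

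**3. Illustration of how far the two tests can part.** The documents give no expected change, so every effect here is assumed. Inputs are 13 per arm (document), two-sided 0.05 (assumed), no drug-specific effect, and the same true change of d SDs of the within-subject change in both arms.

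- Paired test: noncentral t, 12 df, noncentrality d√13, critical value 2.179. For d = 0.5 the noncentrality is 0.5 × 3.606 = 1.803.
- ANCOVA with the baseline value as covariate: 23 df. Simulation with 40,000 runs per cell and baseline to follow-up correlation 0.5, 0.7 and 0.9.
- Significant on liraglutide but not on placebo: p(1 − p), where p is the paired probability.

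| Shared change d | Liraglutide paired test significant | ANCOVA significant | Significant on liraglutide only |
|---|---|---|---|
| 0 | 5% | about 5% | 5% |
| 0.25 | 13% | about 5% | 12% |
| 0.5 | 38% | about 5% | 24% |
| 0.8 | 75% | about 5% | 19% |
| 1.0 | 91% | about 5% | 8% |

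The ANCOVA range over all 15 cells was 4.8% to 5.2%. The last column shows that setting the two arms' p-values side by side is no substitute for the contrast.

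**4. Sensitivity given up.** The smallest difference detectable with 80% power, in change SDs:

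- Paired, n = 13: 3.053/√13 = 0.85.
- ANCOVA, 13 per arm: with equal SDs at both times, the residual SD is the change SD × √((1+ρ)/2). Then 2.926 × √(2/13) = 1.148, and 1.148 × √((1+ρ)/2) gives 0.99 (ρ = 0.5), 1.06 (0.7) and 1.12 (0.9).

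**5. What the ANCOVA needs.** Assume no drug-specific effect but 0.3 SD of extra weight-driven change on liraglutide. The noncentrality is 0.3/(0.392 × 0.866) = 0.88 at ρ = 0.5 and 0.3/(0.392 × 0.975) = 0.78 at ρ = 0.9. The ANCOVA is then significant about 11% to 14% of the time instead of 5%. It isolates a weight-independent effect only if realised weight loss is similar.

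**The case against.** The strongest reply is that the plan already labels its tests. One is marked as within group and the other as the treatment effect. In a randomised two-arm trial, an ANCOVA so labelled is naturally the between-arm test, and the aim and the Treatment section point the same way. A comparison with baseline may also only mean that change from baseline is the outcome, which an ANCOVA can compare between arms. Objective 1, with no comparator, does not contradict this.

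Much of that stands. A reader might infer that no between-arm analysis is planned or that the placebo arm is not used. The documents do not support this: the randomised control and the ANCOVA are both there. A reader might also take the Study Protocol sentence "we will perform kinetic studies on all study subjects before and after the 4-months intervention with the GLP-1 agonist" as leaving placebo out. It refers to all subjects, and the preceding paragraph covers both products and repeats the investigations after treatment, so it is loose wording and no support for this point.

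Nor should the percentages be read as error rates or as the two tests contradicting each other. They address different null hypotheses. When both arms truly change, a significant paired test is a correct rejection. It misleads only if read as a drug-specific effect.

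What does not stand is that the label settles the matter. A two-word parenthesis does not override a primary objective and a secondary lead-in that name baseline as the comparator, and it does not say which test decides.

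**Conclusion.** The point holds as a mismatch between the stated comparisons and the design, with a missing rule on the deciding test. It should be fixed, but it is not a flaw in the design. Objective 2 can be met as worded by a change that cannot test hypothesis 2.

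The textual finding needs no assumption beyond the supplied text. The figures and Appendix A, which the Study Protocol cites for the kinetic analysis, were not available. The size of the consequence is unknown: it is negligible if the change shared by both arms is near zero and large if it nears 1 SD of the within-subject change. The documents do not show where this trial lies in that range.

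The within-arm change remains a legitimate description of drug plus weight loss together. A reader might take it as a test of hypothesis 3. It is not, because it cannot show that weight loss adds to a drug effect.

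**What to change.** 1. For both primary objectives, and for any secondary claim of an effect beyond weight loss, state the comparison as liraglutide versus placebo plus matched weight loss.
2. Name as the deciding test the between-arm ANCOVA on the end-of-treatment value, adjusted for the baseline value of the same endpoint.
3. Keep the paired t-tests, reported for both arms, as descriptive summaries of total within-arm change. Say that they do not test hypothesis 3.
4. State that neither a within-arm p-value nor a comparison of the two arms' p-values supports a drug-specific claim.
5. Report realised weight change by arm, which is already collected, beside the contrast. Confine wording such as beyond weight loss to the case where it is similar, and fix what counts as similar before the analysis.

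The cost is a rewording of the objectives and the statistics paragraph, with no new data. The price is sensitivity: the between-arm contrast will usually look smaller than the change from baseline, and the detectable difference is 0.99 to 1.12 change SDs against 0.85 for the paired test. If the cited 9-per-group figure is a within-subject one, the size statement should also be restated for the between-arm contrast.
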